8.2 Sample Size Considerations

The sample size for this study was selected to have adequate study power to conclude a high NPV of the PCN (B-lactam) allergy history screening questionnaire in ruling out the presence of true PCN (B-lactam) allergy. To address the objective properly, we applied Steinberg's et al.³² approach to obtain the minimal sample size needed to achieve a lower 95% confidence bound for NPV that exceeds the NPV with a useless test at a fixed level of significance with a given study power. Based on this approach, the sample size calculation depends on the prevalence of PCN allergy in the population and among observed study participants and the sensitivity and specificity of the PCN allergy diagnostic kit (PRE-PEN®). To target at least 85% power at 5% of significant level, the listed sample sizes (see table) provide lower 95% confidence bounds for NPV under the following various assumptions:

- The true population prevalence with PCN allergy: 1%, 3%, 5%
- The observed % of PCN allergy in this study: 1%, 3%, 5%
- The PCN allergy diagnostic kit with sensitivity at least 85% and specificity 95%
- 5% of participants who report a PCN allergy history will have a high-risk allergy history and therefore will not proceed to skin testing.

Population prevalence of PCN allergy	Observed % of PCN allergy in study	Estimated NPV	The lower 95% confidence bound for NPV						
			99.0%	98.4%	97.9%	97.5%	97.3%	97.0%	95.0%
1%	1%	99.84%	1259	796	635	556	526	488	351
	3%	99.51%	420	265	212	185	175	163	117
	5%	99.18%	252	159	127	111	105	98	70
3%	1%	99.84%	8119	2964	1958	1559	1421	1259	759
	3%	99.51%	2707	988	653	520	474	420	253
	5%	99.18%	1624	593	392	312	284	252	152
5%	1%	99.84%	113000	9519	4770	3378	2950	2483	1259
	3%	99.51%	37547	3174	1590	1126	984	828	420

	5%	99.18%	22533	1905	954	676	590	497	252
--	----	--------	-------	------	-----	-----	-----	-----	-----

For example, with 3% PCN allergy prevalence in population and among observed study participants, the NPV for a useless test is 97%. A useful PCN (B-lactam) allergy history screening questionnaire should have the lower 95% confidence bound for NPV greater than 97%. Based on the list a minimum sample size of 988 subjects who reported to have PCN allergy history would provide an estimated NPV = 99.51% with 85% power to conclude that the NPV of the study allergy history screening questionnaire is least 98.4% at 5% significant level.

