8.4.1 Primary analysis

The primary analysis will estimate with corresponding exact 95% confidence intervals:

- The prevalence of PCN reactivity validated either by skin test or by direct oral challenge among those participants who report a history of PCN (B-lactam) allergy and who have low-risk histories.
- The NPV on true PCN (B-lactam) allergy of the algorithm / PCN (B-lactam) allergy history screening questionnaire performance in the study population.

The NPV for each question will be estimated and its performance will be assessed.

To construct a short standardized post-study questionnaire (4-6 questions) from the PCN (B-lactam) allergy history screening questionnaire, we will use Item Response Theory (IRT) to evaluate each question item's discrimination ability of true PCN (B-lactam) allergy and use variable importance evaluation functions to indicate which questions are most useful for

predicting the true PCN (B-lactam) allergy. Based on the results of IRT and variable importance analyses, we will then apply machine learning approaches (e.g., random forest approach via R packages of caret)³³ to select a short post-study questionnaire that has the highest NPV among those possible short questionnaires with 4-6 selected questions.

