5. GENERAL STATISTICAL ISSUES

All confidence intervals will be two-sided with 95% coverage. Likewise, all statistical tests will be two-sided and at 0.05 significance level.

Missing data will be treated as missing at random without imputation unless available evidence indicated that missing data is informative. Data at all non-missing time points will be used and included in relevant analyses.

All comparisons between treatment groups will be made without adjustment for multiple comparisons. All statistical analyses will be done using SAS® (SAS Institute Inc., Cary) Version 9.4.

6. Sample Size Consideration

The sample size for this study was selected to have adequate study power to conclude a high NPV of the PCN (B-lactam) allergy history screening questionnaire in ruling out the presence of true PCN (B-lactam) allergy. The approach proposed by Steinberg et al. (2009) is used to obtain the minimal sample size needed to achieve a lower 95% confidence bound for NPV that exceeds the result with a useless test at a fixed level of significance with a given study power. To target at least 85% power at 5% of significant level, the listed sample sizes (see table) provide lower 95% confidence bounds for NPV under the following various assumptions:

- The true population prevalence with PCN allergy: 1%, 3%, 5%
- The observed % of PCN allergy in this study: 1%, 3%, 5%
- The PCN allergy diagnostic kit with sensitivity at least 85% and specificity 95%
- 5% of participants who report a PCN allergy history will have a high-risk allergy history and therefore will not proceed to skin testing.

Population prevalence of PCN allergy	Observed % of PCN allergy in study	Estimate d NPV	The lower 95% confidence bound for NPV						
			99.0%	98.4 %	97.9 %	97.5 %	97.3 %	97.0 %	95.0 %
1%	1%	99.84%	1259	796	635	556	526	488	351
	3%	99.51%	420	265	212	185	175	163	117
	5%	99.18%	252	159	127	111	105	98	70
3%	1%	99.84%	8119	2964	1958	1559	1421	1259	759
	3%	99.51%	2707	988	653	520	474	420	253
	5%	99.18%	1624	593	392	312	284	252	152
5%	1%	99.84%	11600	9519	4770	3378	2950	2483	1259
	3%	99.51%	37547	3174	1590	1126	984	828	420

	5%	99.18%	22533	1905	954	676	590	497	252
--	----	--------	-------	------	-----	-----	-----	-----	-----

A sample of 988 subjects who reported to have PCN allergy history would provide an estimated NPV = 99.51% with 85% power to conclude that the NPV of the study allergy history screening questionnaire is least 98.4% at 5% significant level.

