7.3 Analysis of Primary Objective

The primary analysis will be performed on the Treated population and Per Protocol population. Estimates with corresponding exact (Clopper-Pearson) 95% confidence intervals for the following measures will be provided:

- The prevalence of PCN reactivity validated either by skin test or by direct oral challenge among those participants who report a history of PCN (B lactam) allergy and who have low-risk histories.
- The NPV on true PCN (B-lactam) allergy of the algorithm / PCN (B-lactam) allergy history screening questionnaire performance in the Treated population.

The NPV for each low-risk allergy item listed on the questionnaire will be estimated and will be compared with the prevalence of PCN reactivity using exact test of binomial proportion. The p-values will be adjusted with Benjamini-Hochberg procedure.

To construct a short standardized post-study questionnaire (4-6 questions) from the PCN (B-lactam) allergy history screening questionnaire, we will first use the item-characteristic curve from Item Response Theory (IRT) to evaluate each question item's discrimination ability of true PCN (B-lactam) allergy and use variable importance evaluation functions to indicate which questions are most useful for predicting the true PCN (B-lactam) allergy. Based on the results of IRT and variable importance analyses, we will then apply machine learning approaches such as random forest (Svetnik et al., 2003) via R package caret, to select a short post-study questionnaire that has the highest NPV among those possible short questionnaires with 4-6 selected questions.

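### SAP 7.3 tests each item's NPV against the prevalence of reactivity instead of 1 minus that prevalence, so the item p-values cannot show whether an item beats a useless test

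*SAP*

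**What the plan says.** SAP 7.3 covers the item-level analysis in two steps. First, "The NPV for each low-risk allergy item listed on the questionnaire will be estimated". Then each of these NPVs "will be compared with the prevalence of PCN reactivity using exact test of binomial proportion", and the p-values receive a Benjamini-Hochberg adjustment. The prevalence meant is the first estimand of the same section: the share of low-risk participants who react on skin test or oral challenge.

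Protocol 8.2 states what an uninformative result looks like: "with 3% PCN allergy prevalence in population and among observed study participants, the NPV for a useless test is 97"%. It also gives the direction, since a useful questionnaire "should have the lower 95% confidence bound for NPV greater than 97"%. SAP 6 keeps the same idea without the figure, asking for "a lower 95% confidence bound for NPV that exceeds the result with a useless test".

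Protocol 8.4.1 names no comparator for the items: "The NPV for each question will be estimated and its performance will be assessed". Neither document defines an item-level NPV.

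**The concern.** An item that tells us nothing about allergy has an NPV equal to the non-reactive share of those tested, which is 1 minus prevalence. SAP 7.3 instead sets the null at the prevalence itself, planned at 1%, 3% or 5%. Any realistic item NPV lies far above such a value, so rejection is close to automatic and says nothing about whether the item improves on no information.

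This is the only hypothesis test that SAP 7.3 specifies for the primary objective. A report following it literally would mark useful, useless and misleading history items alike as significant, and readers could take that as evidence that each item is reassuring.

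**Working it through.** **Inputs.** Prevalence 1%, 3% or 5%, sensitivity 85%, specificity 95% and a 5% high-risk share (Protocol 8.2, SAP 6). Two-sided tests at 0.05 (SAP 5).

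**Assumptions.** Item NPV is taken as the non-reactive share of tested participants who report the item. The number of reporters per item is not in the documents, so 100 is used for illustration.

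**Step 1: the plan's own figures.** NPV = sp(1 − p) / [sp(1 − p) + (1 − se)p]. At p = 0.03 this is 0.9215 / (0.9215 + 0.0045) = 0.9951, the stated 99.51%. The useless-test NPV is 1 − 0.03 = 0.97, the stated 97%. At 1% and 5% prevalence the useless-test values are 0.99 and 0.95. The planning section is therefore on the right scale.

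**Step 2: the item test under both nulls.** Two-sided exact binomial p-values, 100 reporters:

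| Item | Non-reactive | Prevalence | p, null = prevalence (as written) | p, null = 1 − prevalence |
|---|---|---|---|---|
| No reactors | 100/100 | 3% | 5.2e-153 | 0.079 |
| Useless | 97/100 | 3% | 2.8e-143 | 1.0 |
| Worse than useless | 90/100 | 3% | 1.1e-124 | 0.0009 (low direction) |
| Useless | 99/100 | 1% | 9.9e-197 | 1.0 |
| Useless | 95/100 | 5% | 1.5e-116 | 1.0 |

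**Step 3: could any item fail to reach significance as written?** Take 950 tested (1,000 less the planned 5% high-risk), hence about 10, 28 or 48 reactors at 1%, 3% or 5%. In the most adverse case every reactor in the study reports the same item, and it has 100 reporters. That leaves 90, 72 or 52 of 100 non-reactive, and p as written is 1.6e-167, 4.9e-86 or 1.9e-40.

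Looking for the smallest number of reporters from which every possible result lies above the null with p ≤ 0.05 gives 12, 32 and 55 (the least favourable counts there are 2/12, p = 0.006; 4/32, p = 0.015; 7/55, p = 0.019). With 1,000 tested the thresholds are 12, 34 and 57.

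**Step 4: multiplicity.** A Benjamini-Hochberg adjusted p-value never exceeds the largest raw p-value. If all raw values are at or below 0.05, so are all adjusted ones. At 0.005, the strictest step for the ten low-risk items (0.05/10), the thresholds with 950 tested become 13, 33 and 57.

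**Step 5: behaviour after correction.** Against 0.97, a truly useless item is rejected at 0.05 with probability 0.031 at 100 reporters and 0.035 at 200, so the level is held. Fisher's test on 950 tested at 3% gives p = 1.0 for a useless item (3/100 against 25/850 reactive) and 0.0003 for a harmful one (10/100 against 18/850).

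**The case against.** The strongest reply is that this is a slip of wording. The team stated the correct benchmark in Protocol 8.2, comparing 1 − NPV with prevalence would be a valid test, and a statistician seeing p-values near 1e-143 would stop. SAP 1 also leaves the table shells to a later version, which gives another chance to catch it. All of that is plausible, but no passage corrects the sentence. SAP 6 leaves out the 97% figure, so someone working from the SAP alone does not have it.

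A second reply is that little depends on these p-values. This is largely right. The short form is chosen "Based on the results of IRT and variable importance analyses", followed by random forest, and the overall NPV and prevalence have their own exact intervals. That limits the weight of the point without making the stated test meaningful.

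Third, Protocol 8.2 sets its benchmark for the whole questionnaire and not for items. Since only low-risk participants are tested, 1 minus the observed prevalence is also the questionnaire's own observed NPV. The corrected item test therefore asks whether reporters of an item do better than the average tested low-risk participant. This stands and should be said in the SAP, but it is still the sensible question for an item.

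Fourth, 950 tested ignores the rule-outs in Protocol 6.1.3 and refusals. That is true; it touches Step 3 and the Fisher thresholds only, while the table in Step 2 does not use it.

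**Conclusion.** The concern holds. As written, the null value of the item test is on the wrong scale, and the documents themselves supply the right one. The p-values still vary with the number of reporters and the result, but they carry no information on whether an item beats a useless test.

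At 3% prevalence and an assumed 100 reporters, a useless item moves from p = 1.0 under the proper null to 2.8e-143. With 950 tested, every item with at least 12, 32 or 55 reporters (1%, 3%, 5% prevalence) is significant whatever its data show. These sizes rest on the assumed reporter counts, number tested and definition of item NPV. The error itself does not, because any NPV is a non-reactive share.

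The item NPV estimates, overall NPV and prevalence intervals, sample size and short-form selection are unaffected. It should be fixed before the analysis is run.

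**What to change.** **Necessary.** In SAP 7.3, define item NPV as the non-reactive share of tested participants reporting the item. Change the comparator to 1 minus the prevalence of reactivity in the same analysis population, and require the direction of any difference to be reported.

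**Preferable, but a choice.** That benchmark is estimated from the same participants, yet a one-sample test treats it as fixed. Comparing reactivity between tested participants who do and do not report the item, by Fisher's exact test with the Benjamini-Hochberg adjustment kept, avoids this. Report each item NPV with its Clopper-Pearson interval.

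**Downside to state in the SAP.** Both corrected tests have low power for rarely reported items. With no reactors among the reporters, p ≤ 0.05 before adjustment needs at least this many reporters:

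| Prevalence | Binomial against 1 − prevalence | Fisher (950 tested; 10, 28 or 48 reactors) |
|---|---|---|
| 1% | 377 | 277 |
| 3% | 126 | 114 |
| 5% | 76 | 67 |

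The intervals should therefore carry the interpretation; 100/100 non-reactive, for example, gives 96.4% to 100%.

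**Cost.** One or two sentences of SAP text. No new data are needed.

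### SAP 7.3 tests each item against a benchmark estimated from the same subjects; once the benchmark is set to 1 − prevalence, the one-sample test loses much power for common items

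*SAP*

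**What the plan says.** Under the primary objective, SAP 7.3 states: "The NPV for each low-risk allergy item listed on the questionnaire will be estimated". Each estimate is then "compared with the prevalence of PCN reactivity using exact test of binomial proportion", and "The p-values will be adjusted with Benjamini-Hochberg procedure". SAP 5 adds that "all statistical tests will be two-sided and at 0.05 significance level".

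The only prevalence that SAP 7.3 defines is the study estimate among low-risk participants: "The prevalence of PCN reactivity validated either by skin test or by direct oral challenge among those participants". Item NPVs and prevalence come from the same analysis sets: "The primary analysis will be performed on the Treated population and Per Protocol population". No external benchmark is set, and no comparison of subjects with and without an item is planned.

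Protocol 8.4.1 is wider in scope and names no test: "The NPV for each question will be estimated and its performance will be assessed". The 4–6 question form is built separately in both documents, from item response theory (IRT), variable importance and a random forest.

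**The concern.** A one-sample binomial test treats its null value as a known constant. Here the null value is an estimate, and the subjects being tested helped to produce it. The more common the item, the more its NPV is tied to the overall value, and the harder it becomes to show a difference even when reactors are concentrated on one side of the item.

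At stake are the prespecified, multiplicity-adjusted item results under the primary objective, which are the plan's only significance statements about single items. If the benchmark value alone were corrected, an informative item that many subjects report could be published as showing nothing.

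There is also a point of scope. The SAP confines item NPVs to the ten low-risk symptom entries of Appendix B question 6, while the protocol speaks of every question. SAP 7.3 gives no reason for the narrowing.

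**Working it through.** **The plan's own figure.** Neither document states a size or power for the item test. The nearest figure is the sample size of 988 (SAP 6), with Se 85%, Sp 95%, prevalence 3%, lower bound 98.4% and power 85%.

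- NPV = 0.95 × 0.97 / (0.95 × 0.97 + 0.15 × 0.03) = 0.99514.
- n = [(1.645 + 1.036) / (logit 0.99514 − logit 0.984)]² × [0.85/(0.15 × 0.03) + 0.05/(0.95 × 0.97)] = (2.681/1.203)² × 188.94 ≈ 939. This uses a one-sided 5% level.
- Dividing by 0.95 for the 5% with a high-risk history gives 988, as stated.

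So about 938 subjects are tested out of 988, or 950 out of the 1,000 evaluable. I use 950 unless noted.

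**The test as literally written.** An NPV near 0.97 is set against a prevalence near 0.03. With 5 of 5 subjects non-reactive, p = 2 × 0.03⁵ ≈ 5 × 10⁻⁸. Almost any item is significant, so what follows applies only after the benchmark becomes 1 − prevalence.

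**Variance.** Let the item be held by n = fN tested subjects and let reactivity be p with no item effect (q = 1 − p).

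- Item proportion − overall proportion = (1 − f) × (item proportion − proportion in the rest).
- Variance = (1 − f)² × [pq/(fN) + pq/((1 − f)N)] = (pq/n) × (1 − f).
- The test assumes pq/n, so its large-sample size is 2 × [1 − Φ(1.96/√(1 − f))]: 0.028, 0.006 and 0.00001 at f = 0.2, 0.5 and 0.8.

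**Exact enumeration.** N = 950, 3% reactive, reactors binomial among subjects with and without the item. For relative risk RR (with versus without), risk without the item is 0.03/(f × RR + 1 − f). At f = 0.5 and RR 1/4 this is 4.8% without and 1.2% with the item. The SAP does not say how the two-sided exact p is formed, so each cell gives doubled one-sided / point-probability, in percent.

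| f | Size: one-sample | Size: Fisher | RR 1/4: one-sample | RR 1/4: Fisher | RR 4: one-sample | RR 4: Fisher |
|---|---|---|---|---|---|---|
| 10% | 1.15 / 2.4 | 1.7 / 3.0 | 2 / 2 | 5 / 6 | 76 / 84 | 79 / 85 |
| 20% | 1.5 / 2.2 | 2.7 / 3.8 | 37 / 38 | 46 / 50 | 86 / 90 | 91 / 93 |
| 30% | 1.1 / 1.4 | 3.1 / 3.9 | 58 / 54 | 70 / 73 | 85 / 90 | 93 / 94 |
| 50% | 0.3 / 0.4 | 3.4 / 3.4 | 72 / 72 | 90 / 90 | 58 / 65 | 90 / 90 |
| 80% | <0.1 / <0.1 | 2.7 / 3.8 | 39 / 38 | 91 / 93 | 0 / 0 | 46 / 50 |

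**After Benjamini-Hochberg** (simulation: 2,000 runs, 938 tested, 3% reactive, ten items with assumed shares of 5–60%), one-sample versus Fisher:

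- f = 50%, RR 1/3: 12% versus 39%.
- f = 50%, RR 3: 1% versus 40%.
- f = 10%, RR 3: 21% versus 27%.

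**An example.** Suppose 28 of 950 react, 760 report the item, and every reactor is among them. The test compares 28/760 = 3.7% with 28/950 = 2.9%, a ratio that cannot exceed 1/f = 1.25. It gives p = 0.24 (point-probability); Fisher's test of 28/760 against 0/190 gives p = 0.003.

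**The case against.** Several objections carry weight.

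- A reader might infer that, as planned, useful items will look uninformative. The text does not support that: against a benchmark near 0.03, nearly every item is significant. The loss of power is a condition on how the benchmark is corrected. This stands.
- A reader might infer that informative questions will be dropped from the short form. SAP 7.3 assigns that choice to IRT, variable importance and a random forest, and nowhere makes the item p-values a gate. This stands.
- A reader might infer that time since reaction, onset, treatment and re-exposure go unassessed. IRT and variable importance cover the question items generally; what these questions lack is an item NPV and a p-value. The protocol promises an NPV and an assessment of performance, not a test. This stands.
- Item frequencies are unknown. The one hint, 76% cutaneous reactions in a cited cohort of military recruits (Protocol 2.2.3), comes from another population and spans several items (itching, rash, older hives, flushing). For rare items the low size is mostly discreteness, which Fisher's test shares: at f = 5%, 2.4% versus 2.7% on the point-probability version. This limits the claim to common items but does not remove it.
- Testing every answer to questions 1–10 would swell the family with about 28 reactors to work from, and holders of higher-risk items are never tested. This stands, and it limits the fix.

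**Conclusion.** The item test in SAP 7.3 is the wrong test for its purpose, and correcting the benchmark alone would leave it wrong. From the table, the power lost against Fisher's test is:

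- at f = 50–80%, about 18 to 55 points, in either direction of effect;
- at f = 30%, about 13 to 20 points for risk-lowering items and 5 to 8 for risk-raising ones;
- at f = 10–20%, about 1 to 5 points for risk-raising items.

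These figures rest on 950 tested, 3% reactive, fourfold risk differences, assumed values of f, and NPV computed among subjects who report the item. The SAP does not define that denominator. If it meant subjects without the symptom, f would be large for rare symptoms and the loss would fall on those instead. At 1% reactive with f = 80% and RR 1/4, power is 5–7% against 42–54%.

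The consequence is confined to the item-level significance results. The narrowing from each question to the low-risk items is a smaller matter: an unexplained difference from Protocol 8.4.1, although Protocol 8.4 says that changes will be documented in the SAP.

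**What to change.** Make the change together with the benchmark correction in SAP 7.3:

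- Replace the one-sample test by Fisher's exact (or a mid-p) test of reactivity in tested subjects with versus without each low-risk item. Name the two-sided convention.
- Report both proportions with exact confidence intervals, and state the denominator of the item NPV.
- Keep Benjamini-Hochberg on the resulting p-values.
- To meet Protocol 8.4.1, also report item NPVs for the closed-form history questions (for example time since reaction, onset, treatment and re-exposure), with one prespecified dichotomy for each.
- Leave out free-text answers and higher-risk items, and say why.

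The cost is a short SAP revision and a few more tests in the Benjamini-Hochberg family. No new data are needed, and the selection of the short questionnaire is unchanged.

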APPENDIX B: PCN (B-LACTAM) ALLERGY HISTORY SCREENING QUESTIONNAIRE

Section 1: Allergy History

- 1) How long ago was the reaction to the antibiotic?
 - a. < 6 months
 - b. 6 months-1 year
 - c. 2-5 years
 - d. 6-10 years
 - e. > 10 years
 - f. Don't remember / Unknown

- 2) What was the name of the drug you reacted to?
 - a. (Please list) _____
 - b. Don't remember / Unknown

- 3) How was the antibiotic administered?
 - a. Pill or Liquid by mouth
 - b. Injection (a shot) into a muscle or through a vein
 - c. Don't remember / Unknown

- 4) When did your allergic reaction to the antibiotic start?
 - a. Less than 1 hour after the first dose
 - b. Between 1 and 6 hours after the first dose
 - c. More than 6 hours, but less than 24 hours after the first dose
 - d. 24 hours or more after the first dose
 - e. Unknown

- 5) How many days did you receive your antibiotic treatment?
 - a. One day only
 - b. About _____ days of treatment
 - c. Don't remember / Unknown

- 6) People experience many different kinds of symptoms during an allergic reaction to an antibiotic. What were the symptoms of your allergic reaction? (OK to select more than one)
 - a. Can't remember (check only after reading entire list)

- b. Non-specific symptom(s) (e.g., "sick" "thought I was a goner" "high as a kite" "like I had the flu")

Responses to the symptoms listed below should be graded on a 5-point scale:

Don't Recall /None / Mild / Moderate / Severe

Low-Risk Allergy History

- a. Isolated GI upset (*diarrhea, nausea, vomiting, abdominal pain*)
- b. Chills (*rigors*)
- c. Headache
- d. Fatigue
- e. Itching (*pruritus*), self-limited,
- f. Rash (*including maculopapular rash*)
- g. Hives (greater than 5 years ago)
- h. Flushing / redness
- i. Family history
- j. Patient denies allergy history but is in medical record

Higher-Risk Allergy History: Skin Testing and Oral Challenge Contraindicated

- a. Angioedema or swelling of lip, tongue, or around eyes
- b. Wheezing / chest tightness moderate or severe shortness of breath
- c. Throat tightness which affected ability to breathe
- d. Hypotension without rapid recovery
- e. Arrhythmia / irregular heartbeat or palpitations
- f. Syncope / pass out / dizzy
- g. Anaphylaxis or sudden drop in blood pressure
- h. Hives (5 years or less)

Late Effect Symptoms (higher-risk events occurred >24 hours after drug administration)

- a. Stevens-Johnson syndrome (*Loss >10% of skin*)
- b. Organ injury (*liver, kidney*)
- c. Low Platelets

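### IRT discrimination is measured against a latent trait, not against the allergy test result, so it should not be an input to choosing the 4-6 question form

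*SAP*

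**What the plan says.** SAP 7.3 gives the item-characteristic curve a specific job. The analysis will "first use the item-characteristic curve from Item Response Theory (IRT) to evaluate each question" item for how well it discriminates true penicillin allergy. Protocol 8.4.1 gives IRT the same job: "we will use Item Response Theory (IRT) to evaluate each question item's discrimination ability of true PCN (B-lactam) allergy". Neither document names the IRT model, defines the latent trait, or says how the skin-test or oral-challenge result enters it.

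IRT is not used alone. The same SAP sentence will also "use variable importance evaluation functions to indicate which questions are most useful for predicting the true PCN (B-lactam) allergy". The next step draws on both: "Based on the results of IRT and variable importance analyses, we will then apply machine learning approaches such as random forest". The final step is to "select a short post-study questionnaire that has the highest NPV among those possible short questionnaires with 4-6 selected questions". No weighting, cut-off or order of precedence between IRT and variable importance is given.

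The raw material is the Appendix B questionnaire, which covers time since the reaction, drug name, route, onset, duration, symptoms, treatment and later re-exposure. For the symptom list, "Responses to the symptoms listed below should be graded on a 5-point scale".

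**The concern.** An item-characteristic curve gives the probability of a response as a function of a latent score, and that score is estimated from the items. In a standard fit the reference result is absent from the likelihood. A steep slope then means that an item agrees with the other items. It means that the item separates reactors from non-reactors only if the items' common trait is allergy.

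The documents give reasons to doubt that it is:

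- Planned prevalence is 1% to 5%, so nearly all of the response pattern comes from people without allergy.
- Protocol 2.1 says the label of allergy is often confused with drug intolerance of any kind.
- Participants with higher-risk symptoms are not tested, so the symptoms most suggestive of allergy should be absent where a reference result exists.
- The items do not obviously form one scale. Family history, and a record of allergy that the patient denies, sit beside symptoms as response options.

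Onset is a plausible casualty. In the predictive-model study described in Protocol 2.2.1, immediate reaction was a significant factor. Onset is Q4, outside the symptom list, so it may share little with the symptom items.

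What is at stake is the validity of one of the two stated inputs to the questionnaire that the primary objective is meant to produce.

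**Working it through.** **Fixing the sample size.** The documents give no figure for the IRT step. The planning figure of 988 (Protocol 8.2, SAP 6) was reproduced only to set the number tested. Inputs: sensitivity se = 0.85, specificity sp = 0.95, population prevalence p = 0.03, observed share k = 0.03, NPV bound 0.984, power 85%, alpha 5%, and 5% not tested.

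- NPV = sp(1−p) / [sp(1−p) + (1−se)p] = 0.9215 / 0.9260 = 0.9951, the plan's 99.51%.
- Variance term = se/[k(1−se)] + (1−sp)/[(1−k)sp] = 188.889 + 0.054 = 188.943.
- Distance = logit(0.016) − logit(0.00486) = −4.119 + 5.322 = 1.203.
- n = (1.645 + 1.036)² × 188.943 / 1.203² ≈ 938.8 tested (unrounded inputs); 938.8 / 0.95 = 988.2, against 988 stated.

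The match needs a one-sided alpha; two-sided gives 1,234. That is a separate matter. The simulations use N = 938.

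**Expected positives.** With 1,000 evaluable participants and 5% untested, 950 are tested. 950 × 1%, 3% and 5% = 9.5, 28.5 and 47.5, so roughly 10 to 48; 938 × 3% = 28.1.

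**How little allergy shapes the trait at 3%.** Assume two items, each endorsed by 20% of non-allergic and 70% of allergic participants. The covariance due to allergy is 0.03 × 0.97 × 0.5 × 0.5 = 0.0073. Marginal endorsement is 0.97 × 0.20 + 0.03 × 0.70 = 0.215, with variance 0.215 × 0.785 = 0.169. The correlation is 0.0073 / 0.169 = 0.04. Any other source of agreement between answers would outweigh it.

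**Simulation.** Ten binary items and a two-parameter logistic IRT model fitted by marginal maximum likelihood; 200 runs per cell. D is true allergy, θ the shared trait. All loadings are assumptions, since the documents give none.

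- A, trait unrelated to allergy: nine items with logit P = −1 + 1.5θ; key item −1.5 + ln(10)·D.
- B, weak overlap: nine items −1 + 1.5θ + ln(1.5)·D; key item −1.5 + 0.5θ + ln(10)·D.
- C, trait is allergy liability: D = 1 when 0.8θ + 0.6e exceeds the prevalence cut-point (e standard normal); nine items −1 + 0.8θ; key item −1.5 + 2.5θ.

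| Scenario | Prevalence | Key item's IRT rank | Mean slope, key vs others | Key item first by odds ratio |
|---|---|---|---|---|
| A | 1% | last in 100% | 0.00 vs 1.51 | 95.5% |
| A | 3% | last in 100% | −0.01 vs 1.51 | 100% |
| A | 5% | last in 100% | 0.00 vs 1.51 | 100% |
| B | 1% | last in 100% | 0.48 vs 1.51 | 88.5% |
| B | 3% | last in 100% | 0.51 vs 1.51 | 100% |
| B | 5% | last in 100% | 0.50 vs 1.51 | 100% |
| C | 1% | first in 100% | 2.54 vs 0.80 | 64.0% |
| C | 3% | first in 100% | 2.56 vs 0.80 | 95.0% |
| C | 5% | first in 100% | 2.55 vs 0.81 | 99.0% |

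In A at 3%, the mean odds ratio for allergy was 10.1 for the key item and 1.0 for the others. A few runs at N = 50,000 gave the same IRT ranks in all three scenarios, so more data does not cure the misranking.

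**Do the plan's other steps recover the item?** A variant of A used N = 950, 3% allergic, and a key item present in 70% of allergic and 20% of other participants. Over 2,000 runs, per-item NPV ranked the key item first in 99.7%. A single-split Gini importance, a rough stand-in for forest importance, ranked it first in 99.95%. So in this setting, where IRT puts the item last, outcome-based measures put it first.

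**The case against.** The strongest reply is that IRT does not decide anything alone. Per-question NPV, variable importance for true allergy, random forest and the highest-NPV choice all use the outcome, and the check above shows that such measures can recover an item that IRT ranks last. This stands, and it limits the point in two ways.

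A reader might infer that IRT is a first filter that eliminates questions. The documents do not support that. The SAP's word first introduces IRT and variable importance in one sentence, the protocol does not use the word there, and neither sets a cut-off. A reader might also infer that the final form will be worse. That has not been shown either, because no simulation here ran the whole selection process.

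The misranking in scenario A also follows from its set-up, and scenario C shows the opposite result. There IRT was steadier than the odds ratio at low prevalence. Binary items simplify the 5-point scale, although a graded model has the same dependence on a latent trait.

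Finally, the sponsor could say that true allergy is the intended trait, since no model is specified. But true allergy is binary. The curve would then reduce to two response proportions, that is, a direct comparison with the reference result, which is what the fix asks for.

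What remains is that a statistic which does not use the outcome is described as measuring discrimination of the outcome, and that no rule applies when it conflicts with variable importance. The backstops also have limits. The SAP confines per-item NPV to the low-risk items, which leaves out Q4, whereas the protocol covers each question. And NPV leaves little room to separate candidate forms: Protocol 8.2 puts a useless test at 97% when prevalence is 3%.

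**Conclusion.** The point holds as a mismatch between method and stated purpose. A standard IRT slope does not measure what SAP 7.3 and Protocol 8.4.1 say it will. It can place a strong allergy predictor last when the items' shared trait is something other than allergy: every run did so in scenarios A and B, none in C. These are illustrative results under assumed loadings, with A as a worst case. Which scenario is closest to the trial cannot be settled from the documents, though the mixed item content and low prevalence make C hard to take for granted. The effect on the final 4-6 question form is unknown, because it depends on an unstated rule for combining IRT with variable importance. The change is worth making before analysis because it is cheap and concerns a product of the primary objective.

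**What to change.** In SAP 7.3 and Protocol 8.4.1, remove IRT from item selection, or keep it as a descriptive summary of item structure that plays no part in the choice.

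Rank items by their association with the reference result among tested (low-risk) participants:

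- Fix the response coding in advance. Q2 is free text and Q6, Q7 and Q9 allow several answers, so sensitivity and specificity are undefined until categories are set.
- Report sensitivity, specificity and likelihood ratios with exact confidence intervals for each coded item.
- Add a penalised logistic coefficient (for example Firth) with few covariates. About 28 positives at 3%, and as few as 10 at 1%, will not support a long list.

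The higher-risk symptom items have no reference result in untested participants and should be left out of this ranking, with a statement saying so.

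Cost: SAP and protocol wording, somewhat different code, and the loss of IRT as a selection input. No new data are needed.
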